### 14.4 Analysis of Secondary Endpoints

As a secondary analysis we will explore if NAC treatment decreases levels of NO in exhaled breath or the numbers of eosinophils in peripheral blood.

### 14.5 Interim Analysis

No interim analysis is planned.

### 14.6 Sample Size

We propose a sample size of 36, which will provide us with the power to examine the effect of NAC in a subgroup of individuals with asthma who have CT evidence of intraluminal mucus and to identify the CT mucus score that performs best as a biomarker of treatment response to NAC. Participants will be enrolled if their CT mucus scores are  $\geq 5.0$ . The sample size is obtained when we factor in an effect size of 5% improvement in FEV1, a standard deviation for change in FEV1 of 20%, a within patient correlation for repeated measures of FEV1 of 0.9, and a power of 90%.

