### **3 STUDY OBJECTIVES**

#### **3.1 Primary Objective**

The primary objective is to determine if inhaled NAC decreases mucus plugs and improves lung function in patients with asthma.

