#### **3.2 Secondary Objectives**

The secondary objective is to determine the duration of benefit of inhaled NAC in asthma and identify characteristics of those subjects who benefit from mucolytic treatment.

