## 5.2 Secondary Efficacy Endpoints

We intend to examine the effect of the treatment on CT mucus score, however, because the CT mucus score is a novel measurement, we do not have preliminary data to describe the natural history of mucus in the airway over time or with treatment. Therefore, for the purpose of this study, we intend to describe any changes we observe.

Other Secondary efficacy endpoints will include:

- FVC
- PEF (AM and PM)
- Air trapping (RV/TLC ratio)
- FeNO
- Blood eosinophils

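### Section 14.6 claims power for a CT mucus score biomarker, but 36 patients is sized only for the mean FEV1 comparison

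*Combined protocol and SAP*

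**What the plan says.** Section 14.6 opens: "We propose a sample size of 36, which will provide us with the power to examine the effect of NAC in a subgroup" of asthma patients with mucus on CT, and adds a second purpose, "to identify the CT mucus score that performs best as a biomarker of treatment response to NAC". The inputs that follow are "an effect size of 5% improvement in FEV1", "a standard deviation for change in FEV1 of 20" percent, a within-patient correlation of 0.9 and 90% power. On entry it says: "Participants will be enrolled if their CT mucus scores are" 5.0 or higher.

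Two objectives bear on the same point.

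- **Mucus plugs.** Section 3.1 sets out to "determine if inhaled NAC decreases mucus plugs and improves lung function in patients with asthma". Section 5.2 lists CT mucus score as a secondary endpoint. It explains that the measure is new and has no preliminary data on change, and concludes: "for the purpose of this study, we intend to describe any changes we observe". Section 14.3 adds an analysis relating change in FEV1 to change in CT score, with no method stated. Section 14.4 names only exhaled NO and blood eosinophils.
- **Duration.** Section 3.2 states: "The secondary objective is to determine the duration of benefit of inhaled NAC in asthma", together with finding out which patients benefit. Neither 5.2 nor 14.4 contains an endpoint or analysis for duration.

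Section 14 promises a detailed SAP before the final analysis.

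**The concern.** A power statement tells the reader which questions the trial was built to answer. Section 14.6 attaches one calculation to two questions: whether NAC changes FEV1 on average, and which CT score best predicts who responds. The second concerns differences in treatment effect between patients, which usually takes many more patients than a mean effect does. If the wording stands, a score or cut-off found in 36 patients could be read as coming from a trial powered to find it.

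The two objectives raise a related problem: what they promise goes beyond the planned analysis (mucus plugs) or the visit schedule (duration).

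**Working it through.** **1. Reproducing 36.** Inputs from 14.6: effect 5, SD 20, correlation 0.9, power 90%. Alpha is not stated; I assume 0.05 two-sided.

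- SD of the within-patient difference = 20 × √(2 × (1 − 0.9)) = 8.94.
- Normal approximation: n = ((1.960 + 1.282) × 8.94 / 5)² = 33.6, so 34.
- Exact paired t-test (noncentral t): n = 36, power 90.3%.

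The stated inputs therefore account for all 36 patients through the FEV1 comparison.

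**2. What 36 gives the biomarker question.** The documents give no biomarker effect, so the following are assumptions: two-sided 0.05; response defined as each patient's NAC-placebo difference in % change in FEV1; SD 8.94.

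*Score as a continuous predictor (Fisher z).*
- Detectable correlation at 90% power: r = tanh((1.960 + 1.282) / √(36 − 3)) = 0.51. At 80% power it is 0.45.
- Power is 43% at r = 0.3 and 68% at r = 0.4. For 90% power these need 113 and 62 patients.

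*Two halves, 18 v 18, fixed in advance (two-sample t, 34 df).*

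| SD of NAC-placebo difference | Difference needed for 90% power | Power for a 5-point difference |
|---|---|---|
| 8.94 (plan's inputs) | 9.95 points | 37% |
| 12.65 (assumed: correlation 0.8, 20 × √0.4) | 14.07 points | 21% |

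The 5-point difference between halves is my choice, set equal to the planned mean effect. With SD 8.94, an uneven split lowers power for it to 34% (12 v 24) or 29% (9 v 27). By the normal approximation, 90% power needs 68 patients per side, 136 in all.

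*Searching for the best cut-off.* I assume scores spread evenly over 5 to 20, 15 candidate cut-offs and at least 5 patients per side. In simulation, with no true biomarker effect, about 24% of trials yield at least one nominal p < 0.05. With a true 5-point step, the selected cut-off falls within one unit of the true one in about 43% of trials.

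**3. Range of scores.** Entry requires a score of 5 or more, so 5 or above cannot be compared with below 5. Higher cut-offs can be explored.

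**4. Mucus plugs.** CT is scheduled at Visits 3, 6, 7 and 10 (section 8.1.14), before and after each treatment period. That gives every completer a change on NAC (Visit 3 to 6 or 7 to 10) and a change on placebo. The data for a within-patient comparison are collected; no such comparison is planned.

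**5. Duration.** Period 1 treatment ends at Visit 6 (Day 21). The next visits are Visit 7 (Day 77, 56 days or 8 weeks later) and Visit 8 (Day 84, 63 days or 9 weeks later, when period 2 dosing starts). Visit 10 (Day 98) ends both period 2 and the schedule. With 1:1 allocation, about 18 NAC-first patients have measurements after NAC has stopped, at 8 and 9 weeks only. The other 18 or so have none.

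For a comparison between sequences of FEV1 change from Visit 4 to Visit 7, the 95% CI half-width is 2.032 × SD × √(2/18). This is 6.1 points if the SD of that change is 8.94, and 13.5 points if it is 20. Which SD applies is an assumption.

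**The case against.** The strongest reply has four parts.

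- **The calculation is sound for its main purpose.** This stands. A reader might infer that 36 is wrong for FEV1, but on the stated inputs it reproduces.
- **The biomarker aim can still be explored.** This stands too. A reader might infer that the entry limit defeats the aim altogether. It does not: scores above 5 vary and can be related to response. Only the entry threshold itself is beyond reach. Nor do the documents say that a cut-off will be reported as a powered result. The fault is the claim of power.
- **The mucus-plug question is within the design.** Correct. A reader might infer that the trial cannot answer it, or that CT change is merely described. The first is contradicted by a randomised, double-blind crossover with scans around each treatment. The second overlooks the FEV1-CT analysis in 14.3. Section 5.2 also gives a reason for description: there are no preliminary data. That excuses the lack of a power calculation. It does not reconcile description only with a place in the primary objective, and 14.3 does not compare NAC with placebo on CT score. It concerns change in score, so it does not test baseline score as a predictor either.
- **A later SAP can supply the detail.** It can add models. It cannot make the power statement in 14.6 true, and it cannot add off-treatment visits.

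**Conclusion.** The biomarker power statement in 14.6 is wrong as written. All the stated power belongs to the mean FEV1 comparison. On the plan's implied SD of 8.94 and two-sided 0.05, 36 patients reach 90% power for a biomarker only with a correlation near 0.51 or a difference of about 10 points between halves, twice the planned mean effect. A 5-point difference has about 37% power, and less if the SD is larger. The alpha, the equal split and the 5-point difference are assumptions; the documents fix none of them.

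The two related points are narrower. The mucus-plug objective lacks a planned between-treatment comparison that the design could support. The duration objective cannot be met: the schedule can show at most whether a difference remains about 8 weeks after stopping, and any such difference is also the carryover that the synopsis analysis plan needs to be negligible. None of this invalidates the primary FEV1 test, so the correction is advisable rather than critical.

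**What to change.** **Section 14.6.** Delete the biomarker power statement and say that 36 is sized for the FEV1 comparison only. Call the biomarker aim exploratory: a regression of each patient's NAC-placebo difference in % change in FEV1 on baseline (Visit 3) CT score, reported with a confidence interval. Label any cut-off as hypothesis-generating, and state that the entry threshold cannot be evaluated.

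**Sections 3.1, 5.2 and 14.4.** Add a within-patient NAC v placebo comparison of change in CT score (Visit 3 to 6 and Visit 7 to 10), with a confidence interval and a period term. The period term is needed because selection on the entry score can cause regression to the mean in period 1. The current plan, a paired t-test, has no such term.

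**Section 3.2.** Restate duration as whether an FEV1 difference between sequences persists about 8 weeks after stopping (Visit 4 to Visit 7, with a confidence interval). Note beside it that such persistence is the same thing as carryover, so that the two results are read together.

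**Cost.** More modest claims, some rewording and a few small analyses of data already collected. No extra patients, visits or scans.

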## DATA COLLECTION, RETENTION AND MONITORING

### 14.7 Data Collection Instruments

The Investigator will prepare and maintain adequate and accurate source documents designed to record all observations and other pertinent data for each participant treated with the study drug.

Study personnel at each site will enter data from source documents corresponding to a participant's visit into the protocol-specific paper CRF when the information corresponding to that visit is available. Participants will not be identified by name in the study database or on any study documents to be collected by the Sponsor (or designee), but will be identified by a site number, participant number and initials.

The Investigator is responsible for all information collected on participants enrolled in this study. All data collected during the course of this study must be reviewed and verified for completeness and accuracy by the Investigator. A copy of the CRF will remain at the Investigator's site at the completion of the study.

### 14.8 Data Management Procedures

The data will be entered into a validated database. The Data Management group will be responsible for data processing, in accordance with procedural documentation. Database lock will occur once quality assurance procedures have been completed.

All procedures for the handling and analysis of data will be conducted using good computing practices meeting FDA guidelines for the handling and analysis of data for clinical trials.

#### **14.9 Data Quality Control and Reporting**

After data have been entered into the study database, a system of computerized data validation checks will be implemented and applied to the database on a regular basis. Query reports (Data Clarification Requests) pertaining to data omissions and discrepancies will be forwarded to the clinical research coordinators for resolution. The study database will be updated in accordance with the resolved queries. All changes to the study database will be documented.

#### **14.10 Archival of Data**

The database is safeguarded against unauthorized access by established security procedures; appropriate backup copies of the database and related software files will be maintained. Databases are backed up by the database administrator in conjunction with any updates or changes to the database.

At critical junctures of the protocol (e.g., production of interim reports and final reports), data for analysis is locked and cleaned per established procedures.

#### **14.11 Availability and Retention of Investigational Records**

The Investigator must make study data accessible to the monitor, other authorized representatives of the Sponsor (or designee), IRB/IEC, and Regulatory Agency (e.g., FDA) inspectors upon request. A file for each participant must be maintained that includes the signed Informed Consent, HIPAA Authorization and Assent Form and copies of all source documentation related to that participant. The Investigator must ensure the reliability and availability of source documents from which the information on the CRF was derived.

All study documents (patient files, signed informed consent forms, copies of CRFs, Study File Notebook, etc.) must be kept secured for a period of two years following marketing of the investigational product. There may be other circumstances for which the Sponsor is required to maintain study records and, therefore, the Sponsor should be contacted prior to removing study records for any reason.

#### **14.12 Monitoring**

Monitoring visits will be conducted by representatives of the Sponsor according to the U.S. CFR Title 21 Parts 50, 56, and 312 and ICH Guidelines for GCP (E6). By signing this protocol, the Investigator grants permission to the Sponsor (or designee), and appropriate regulatory authorities to conduct on-site monitoring and/or auditing of all appropriate study documentation.

#### **14.13 Participant Confidentiality**

In order to maintain participant confidentiality, only a site number, participant number and participant initials will identify all study participants on CRFs and other documentation.

Additional participant confidentiality issues (if applicable) are covered in the Clinical Study Agreement.

## **15 ADMINISTRATIVE, ETHICAL, REGULATORY CONSIDERATIONS**

The study will be conducted according to the Declaration of Helsinki, Protection of Human Volunteers (21 CFR 50), Institutional Review Boards (21 CFR 56), and Obligations of Clinical Investigators (21 CFR 312).

To maintain confidentiality, all laboratory specimens, evaluation forms, reports and other records will be identified by a coded number and initials only. All participant interviews/visits are conducted in private testing rooms. Information about study participants is kept in binders in a locked storage closet, and in our password protected secure electronic files, and is only accessible to authorized study personnel. Clinical information will not be released without written permission of the participant, except as necessary for monitoring by the FDA. The Investigator must also comply with all applicable privacy regulations (e.g., Health Insurance Portability and Accountability Act of 1996, EU Data Protection Directive 95/46/EC).

### **15.1 Protocol Amendments**

Any amendment to the protocol will be written by the Sponsor. Protocol amendments cannot be implemented without prior written IRB/IEC approval except as necessary to eliminate immediate safety hazards to patients. A protocol amendment intended to eliminate an apparent immediate hazard to patients may be implemented immediately, provided the IRBs are notified within five working days.

### **15.2 Institutional Review Boards and Independent Ethics Committees**

The protocol and consent form will be reviewed and approved by the IRB/IEC of each participating center prior to study initiation. Serious adverse experiences regardless of causality will be reported to the IRB/IEC in accordance with the standard operating procedures and policies of the IRB/IEC, and the Investigator will keep the IRB/IEC informed as to the progress of the study. The Investigator will obtain assurance of IRB/IEC compliance with regulations.

Any documents that the IRB/IEC may need to fulfill its responsibilities (such as protocol, protocol amendments, Investigator's Brochure, consent forms, information concerning patient recruitment, payment or compensation procedures, or other pertinent information) will be submitted to the IRB/IEC. The IRB/IECs written unconditional approval of the study protocol and the informed consent form will be in the possession of the Investigator before the study is initiated. The IRB/IECs unconditional approval statement will be transmitted by the Investigator to prior to the shipment of study supplies to the site. This approval must refer to the study by exact protocol title and number and should identify the documents reviewed and the date of review.

Protocol and/or informed consent modifications or changes may not be initiated without prior written IRB/IEC approval except when necessary to eliminate immediate hazards to the patients or when the change(s) involves only logistical or administrative aspects of the

study. Such modifications will be submitted to the IRB/IEC and written verification that the modification was submitted and subsequently approved should be obtained.

The IRB/IEC must be informed of revisions to other documents originally submitted for review; serious and/or unexpected adverse experiences occurring during the study in accordance with the standard operating procedures and policies of the IRB; new information that may affect adversely the safety of the patients of the conduct of the study; an annual update and/or request for re-approval; and when the study has been completed.

### **15.3 Informed Consent Form**

Informed consent will be obtained in accordance with the Declaration of Helsinki, ICH GCP, US Code of Federal Regulations for Protection of Human Subjects (21 CFR 50.25[a,b], CFR 50.27, and CFR Part 56, Subpart A), the Health Insurance Portability and Accountability Act (HIPAA, if applicable), and local regulations.

The Investigator will prepare the informed consent form, assent and HIPAA authorization and provide the documents to the IRB/IEC for approval prior. The consent form generated by the Investigator must be approved by the IRB/IEC. The written consent document will embody the elements of informed consent as described in the International Conference on Harmonisation and will also comply with local regulations.

A properly executed, written, informed consent will be obtained from each participant prior to entering the participant into the trial. Information should be given in both oral and written form and participants must be given ample opportunity to inquire about details of the study. A copy of the signed consent form will be given to the participant and the original will be maintained with the participant's records.

### **15.4 Publications**

The preparation and submittal for publication of manuscripts containing the study results shall be in accordance with a process determined by mutual written agreement among the study Sponsor and participating institutions. The publication or presentation of any study results shall comply with all applicable privacy laws, including, but not limited to, the Health Insurance Portability and Accountability Act of 1996.

### **15.5 Investigator Responsibilities**

By signing the Agreement of Investigator form, the Investigator agrees to:

1. Conduct the study in accordance with the protocol and only make changes after notifying the Sponsor (or designee), except when to protect the safety, rights or welfare of participants.
2. Personally conduct or supervise the study (or investigation).
3. Ensure that the requirements relating to obtaining informed consent and IRB review and approval meet federal guidelines, as stated in § 21 CFR, parts 50 and 56.
4. Report to the Sponsor or designee any AEs that occur in the course of the study, in accordance with §21 CFR 312.64.

5. Ensure that all associates, colleagues and employees assisting in the conduct of the study are informed about their obligations in meeting the above commitments.
6. Maintain adequate and accurate records in accordance with §21 CFR 312.62 and to make those records available for inspection with the Sponsor (or designee).
7. Ensure that an IRB that complies with the requirements of §21 CFR part 56 will be responsible for initial and continuing review and approval of the clinical study.
8. Promptly report to the IRB and the Sponsor (or designee) all changes in the research activity and all unanticipated problems involving risks to participants or others (to include amendments and IND safety reports).
9. Seek IRB approval before any changes are made in the research study, except when necessary to eliminate hazards to the patients/ participants.
10. Comply with all other requirements regarding the obligations of clinical investigators and all other pertinent requirements listed in § 21 CFR part 312.

#### Appendix A. Schedule of Study Visits (UCSF)

Visit	1	2a	2b*	3	4	5	6 	7	8	9	10
Time Commitment (hours)**	2	2	3	2	8	2	4	4	8	2	4
Consent and eligibility	x										
Questionnaires	x				x	x	x	x	x	x	x
Physical Exam	x				x 	x 	x 		x 	x 	x 
Vital signs & oximetry	x	x	x	x	x	x	x	x	x	x	x
FENO					x	x	x		x	x	x
Spirometry	x	x	x	x	x	x	x	x	x	x	x

Post-bronchodilator reversibility		x		x	x	x	x	x	x	x	x
Methacholine challenge			x								
Urine pregnancy test	x	x	x		x	x			x	x	
Sputum induction		x	x				x	x			x
Blood sample					x 		x	x			x
Plethysmography					x		x		x		x
CT thorax				x			x	x			x
Nebulizer & diary card education & teach-back					x				x		
Medication administration					x	x			x	x	
Randomization					x						

\* Participation in visit 2b is dependent on post-bronchodilator reversibility test results obtained at visit 2a.

The visit 2 sputum induction will only be obtained at visit 2a or 2b.

\*\*Duration of visit is an estimation

1. Blood sample to include DNA, plasma, serum and CBC with 5-part differential
2. Abbreviated physical exam.

## Appendix B. Schedule of Study Visits (UC Davis)

Visit	1	2a	2b*	3	4	5	6	7	8	9	10
Time Commitment (hours)**	2	2	3	2	8	2	4	4	8	2	4
Consent and eligibility	x										
Questionnaires	x				x	x	x	x	x	x	x
Physical Exam	x				x 	x 	x 		x 	x 	x 
Vital signs & oximetry	x	x	x	x	x	x	x	x	x	x	x
FENO					x	x	x		x	x	x
Spirometry	x	x	x	x	x	x	x	x	x	x	x
Post-bronchodilator reversibility		x		x	x	x	x	x	x	x	x
Methacholine challenge			x								
Urine pregnancy test	x	x	x		x	x			x	x	
Blood sample					x		x	x			x
Plethysmography					x		x		x		x
CT thorax				x			x	x			x
Nebulizer & diary card education & teach-back					x				x		
Medication administration					x	x			x	x	
Randomization					x						

\* Participation in visit 2b is dependent on post-bronchodilator reversibility test results obtained at visit 2a.

The visit 2 sputum induction will only be obtained at visit 2a or 2b.

\*\*Duration of visit is an estimation

1. Abbreviated physical exam.

